This trial will be conducted in accordance with the protocol, Michigan Institute for Clinical & Health Research (MiCHR) Terms and Conditions of Award, applicable local and federal regulatory requirements and best research practices. The Principal Investigator will assure that no deviation from, or changes to the protocol will take place without prior agreement from the funding agency and documented approval from the Institutional Review Board (IRB), except where necessary to eliminate an immediate hazard(s) to the trial participants. All personnel involved in the conduct of this study have completed Human Subjects Protection and ICH GCP Training.

[figure not shown]
1 PROTOCOL SUMMARY

1.1 SYNOPSIS

[figure not shown]
Title:	Implementation of a Diagnostic Stewardship Bundle for Ventilator-associated Pneumonia among Mechanically-ventilated patients: a pilot/feasibility trial.
Grant Number:	Not applicable
Study Description:	A pilot/feasibility trial to evaluate the safety and efficacy of a multi-faceted ventilator-associated pneumonia diagnostic stewardship bundle. Trial ICUs will sequentially implement interventions targeting the respiratory culture diagnostic testing pathway to minimize diagnostic error and overtreatment of ventilator-associated pneumonia.
Objectives:	
Primary Objective: To determine the safety of a multi-faceted ventilator-associated pneumonia diagnostic stewardship bundle.
 
Secondary Objectives:
 
- To determine the association between a multi-faceted ventilator-associated pneumonia diagnostic stewardship bundle and ICU antibiotic utilization rates.- To determine the association between a multi-faceted ventilator-associated pneumonia diagnostic stewardship bundle and rates of positive respiratory cultures.
Endpoints:	To assess study feasibility and adherence to protocolized intervention.
	
Primary Endpoints:
 
- Mortality per 1000 mechanically-ventilated patient days- Ventilator-associated events (using Centers for Disease Control/National Healthcare Safety Network definitions) per 1000 patient days- Median duration of mechanical ventilation per patient.
	
Secondary Endpoints:
 
- Positive respiratory cultures per 1000 mechanically-ventilated patient days.- Total ICU antibiotic utilization rates (total antibiotic days of therapy per 1000 mechanically-ventilated patient days).- Broad-spectrum ICU antibiotic utilization rates (broad-spectrum antibiotic days of therapy per 1000 mechanically-ventilated patient days).- Respiratory cultures ordered per 1000 patient days.- Percentage of respiratory cultures obtained by BAL.- Percentage of respiratory cultures from BAL samples with alveolar neutrophils <50% (for Phase 2 only)
Study Population:	All mechanically-ventilated patients hospitalized within Michigan Medicine Cardiac Care Unit (CCU) and Critical Care Medicine Unit (CCMU).

Phase or Stage:	Pilot/feasibility trial of a population-based intervention.
Description of Sites/Facilities Enrolling Participants:	2 Michigan Medicine Intensive Care units.
Description of Study Intervention/Experimental Manipulation:	A multi-faceted diagnostic stewardship bundle targeting the ventilator-associated pneumonia respiratory culture testing pathway. Three interventions will be operationalized in sequential intervals at the following phases of the diagnostic testing pathway: ordering, collection, and reporting.
Study Duration:	2 years.
Participant Duration:	Not applicable.

1.2 SCHEMA

1.3 STUDY TIMELINE

2 INTRODUCTION

2.1 STUDY RATIONALE

Indiscriminate use of antibiotics is a leading cause of adverse drug events and a catalyst for emergence of multidrug-resistant organisms (MDROs), which account for 2.8 million infections and 37,000 deaths annually in the US.^{1,2} Antimicrobial stewardship programs are instrumental in curbing antibiotic overuse, but their reach into intensive care units (ICUs)—where antibiotic resistance is most prevalent and problematic—is limited.³⁻⁵ Treatment for suspected respiratory infection, in particular, ventilator-associated pneumonia (VAP), accounts for 50-70% of antibiotic use within ICUs.⁶⁻⁹ Studies using multidisciplinary expert case review or autopsy findings as reference gold standards demonstrate that a majority of ICU patients treated for VAP are misdiagnosed, resulting in excessive and often unnecessary antimicrobial exposure, adverse drug events, and generation of MDROs.¹⁰⁻¹³ **There is a pressing need to identify strategies to reduce unnecessary antibiotic use against misdiagnosed VAP in ICUs.**

2.2 STUDY BACKGROUND

Antibiotic overuse is an increasingly recognized problem in intensive care units (ICUs).^{9,14} A recent multinational point-prevalence study of 1150 ICUs determined that 70% of patients surveyed were receiving antibiotics; only 54% of these patients had suspected or proven infection and only 35% had positive microbiologic cultures supporting a definitive diagnosis of infection.¹⁵ Excess antibiotic use catalyzes the acquisition and spread of multidrug-resistant organisms (MDROs), which have risen precipitously within ICUs in recent decades and are associated with excess morbidity, mortality, and healthcare expense.¹⁶⁻²³ Antibiotic overuse is also associated with adverse patient outcomes, including *Clostridioides difficile* infection, drug toxicity, and incident sepsis, as well as increases in healthcare costs and length of stay.²⁴⁻²⁸

Treatment for suspected respiratory infection—in particular, ventilator-associated pneumonia (VAP)—accounts for 50-70% of antibiotic use within ICUs.⁶⁻⁹ **Multidisciplinary case review and autopsy studies demonstrate that a substantial number of ICU patients treated for VAP are misdiagnosed, resulting in significant antimicrobial overuse.**^{10-13,29,30} For example, a multidisciplinary review of 231 cases diagnosed and treated as VAP in 6 ICUs at Johns Hopkins Hospital determined that antibiotics were not indicated in 59% of cases at the time of diagnosis, resulting in 1,183 days of unnecessary antibiotic use over 1 year.¹⁰ A similar multidisciplinary review of surgical ICUs at Johns Hopkins Hospital found that fewer than 25% of patients empirically treated for postoperative VAP met standardized criteria for infection, accounting for 1,460 days of inappropriate antibiotic therapy over 1 year.¹¹ At Michigan Medicine University Hospital, a review of patients with positive respiratory cultures who were treated for nosocomial pneumonia determined that 34% were misdiagnosed, account for a median of 12 excess days of unnecessary antibiotics per patient.³⁰

Most efforts to curb inappropriate VAP-directed antibiotic use have focused on therapeutic processes, namely antibiotic discontinuation or de-escalation strategies, for patients with an established VAP diagnosis.³¹⁻³⁹ These strategies have been largely unsuccessful in curbing antibiotic overuse. To date, no efforts have instead addressed the diagnostic process for VAP—interventions targeting the pathway of ordering, collection, and reporting of diagnostic tests to proactively avert unnecessary antibiotic use in patients with low pretest probabilities of infection (Figure 1).⁴⁰ Interventions targeting the diagnostic testing pathway for infectious syndromes—collectively termed diagnostic stewardship approaches—have been shown to avert unnecessary antibiotic treatment of conditions such as asymptomatic bacteriuria and *Clostridioides difficile* colonization but remain unexplored in VAP.⁴⁰⁻⁴⁹

[figure not shown]

Figure 1: Schematic Representation of Diagnostic vs Antimicrobial Stewardship.

A foundational component of the VAP diagnostic pathway is the collection and interpretation of respiratory cultures. Positive respiratory cultures inform the diagnostic probability of VAP, but by themselves are not synonymous with infection, owing to the high burden of bacterial colonization of endotracheal tubing and distal lung parenchyma in critically ill patients.⁵⁰⁻⁵³ Respiratory bacterial colonization with pathogenic organisms has been reported in over 50% of patients requiring intensive care and in up to 90% of patients with prolonged ventilator-dependence.^{52,53} Indeed, advances in microbiologic techniques have shown that the lungs, once considered sterile, in fact house diverse bacterial communities.⁵⁴ **Contemporary respiratory culturing practices frequently identify bacteria from the respiratory tract of critically-ill patients without pneumonia and are a major factor in inciting unnecessary antibiotic use.**^{10,39,55} Novel interventions targeting the respiratory culture testing pathway therefore represent an attractive and, to date, unexplored target for stewardship interventions to proactively decrease antibiotic use.

[figure not shown]

Figure 2. VAP Diagnostic Stewardship Bundle. EMR=electronic medical record, RC=respiratory culture, RT=respiratory therapist, PMN%=polymorphonuclear cell percentage of alveolar cytology below):

Using an approach patterned on validated diagnostic stewardship interventions for asymptomatic bacteriuria, our group has identified interventions at each of the three phases of the VAP microbiologic diagnostic pathway (test ordering, sample collection and result reporting) to lower antibiotic overuse among mechanically-ventilated patients (Figure 2, see details below):

1. Ordering (preanalytic) phase:

- *Current state:* At present, there are no preconditions for ordering respiratory cultures; as a result, respiratory cultures are often ordered indiscriminately and in scenarios of uncertain or low utility: for surveillance purposes following tracheostomy placement, following transient clinical decompensations which resolve expediently with supportive care (i.e. mucous plugging events), for isolated changes in endotracheal secretion character, as as part of a “pan-culture” workup in response to fever or leukocytosis.^{30,56,57,58} We have demonstrated that these practices incent unnecessary antibiotic use and are common at our institution.³⁰ Additionally, approximately 10% of respiratory cultures ordered in ICUs are “repeat cultures”—tests that are drawn within 72 hours of an identical test (internal data).

While a positive respiratory culture in the context of fever informs the diagnostic probability of pneumonia, it is exceedingly unlikely to indicate VAP in patients without localizing pulmonary features of infection. For example, if one assumes a VAP prevalence of 10% among mechanically-ventilated patients,²¹ those with fever but without new radiographic infiltrates, alterations in gas exchange or purulent sputum have a pretest probability of VAP prior to respiratory culture of 2.6%; a positive respiratory culture would increase the posttest probability of VAP to 3.7%, rendering the test minimally beneficial at best.⁵⁰ Our group has shown that procuring respiratory cultures in patients identified above is associated with excessive antibiotic utilization within just one week of respiratory culture collection.⁵⁹

2. Collection (analytic) phase:

- *Current state:* There is wide variability in ICU practice patterns for acquiring respiratory specimens. 60% of respiratory cultures in ICUs at our institutional are obtained from proximal lung samples, most frequently via endotracheal aspiration (ETA). ETAs are convenient to acquire, but growth of microorganisms from ETA adds little to the diagnostic specificity of VAP, as pathogenic organisms often colonize endotracheal material within hours of intubation.⁶⁰⁻⁶² ETA samples demonstrate low concordance with organisms isolated from the lung itself in both animal models and human studies.^{62,63} Distal lung sampling, via bronchoalveolar lavage (BAL), offers the advantage of directly sampling the alveolar space and can be performed without bronchoscopic guidance by Respiratory Therapists at Michigan Medicine for equivalent supply and labor cost to ETAs. In multiple randomized controlled trials, use of BAL rather than ETA for respiratory collection in suspected VAP has been associated with lower rates of antibiotic use, without increased rates of mortality or ventilator-dependence.⁶⁴⁻⁶⁷

3. Reporting (postanalytic) phase:

- *Current state:* Physicians routinely utilize the number and proportion of white blood cells recovered from bodily fluid to determine the significant of positive culture results (for example, this is considered standard of care in ascites fluid, pleural fluid and urine). Using this data from clinical specimens helps providers to differentiate infection from contamination when a clinical culture grows bacteria. For example, if a patient grows bacteria from a urine specimen, but the patient’s urine has few to no white blood cells present, it virtually assures that the bacteria recovered is not causing a clinical infection. In a VAP enriched population of 851 ICU patients, our collaborators have demonstrated that BAL neutrophil percentage <50% has a negative predictive value of 92% for ruling out VAP.⁶⁸ Autopsy studies have similarly shown that BAL neutrophil percentage <50% approaches a sensitivity of 100% in ruling out infection.⁶⁹ Despite this, alveolar neutrophilia has never been adopted for diagnostic stewardship purposes. Similarly, all respiratory cultures include

a gram stain to identify bacteria under a microscope. If one assumes a VAP prevalence of 20-30%, the negative predictive value of a negative gram stain for VAP diagnosis is 91%. Despite this, negative gram stains are not routinely used by providers to inform interpretation of respiratory cultures.

The manner in which test results are reported by microbiology labs has been shown to significantly impact antibiotic use. Strategies such as “cascading” and selective reporting of antimicrobial susceptibility results, adding comments to microbiologic test results (to “nudge” providers towards appropriate antimicrobial prescriptions), and censoring tests results in certain clinical scenarios (such as growth of likely contaminant organisms from blood cultures or growth of pathogenic bacteria in urine without pyuria) have all shown success as diagnostic stewardship strategies.^{41,70}

Our goal is to conduct a pilot/feasibility trial of this VAP diagnostic stewardship bundle within Michigan Medicine ICUs to 1) demonstrate concept feasibility, 2) gauge and address protocol adherence, and 3) collect preliminary data pertaining to intervention efficacy and safety. **A successful VAP diagnostic stewardship bundle has the potential to significantly lower inappropriate ICU antibiotic use and consequent rates of antimicrobial resistance while simultaneously providing an innovative blueprint for future ICU stewardship interventions.**

3 RISK/BENEFIT ASSESSMENT

3.1.1 Known Potential Risks

This study’s intervention is aimed at reducing overtesting/overdiagnosis and their consequent harms to patients. A potential concern for any intervention aimed at lowering overdiagnosis is the possibility of *underdiagnosis*. This is of particularly importance for VAP which is a condition associated with substantial morbidity and mortality.²¹ Expedient performance of respiratory cultures and receipt of susceptibility test results is a key component of VAP management and delays in effective antimicrobial therapy are important determinants of outcomes.^{71,72}

3.1.2 Known Potential Benefits

Reduction of unnecessary antibiotic use has been associated with significant benefits to patients and healthcare systems. For patients, these include lower rates of *Clostridioides difficile* infection, adverse drug events and incident sepsis. For healthcare systems, reduction of unnecessary antibiotic use has been consistently associated with decreases in hospital-wide rates of multi-drug resistant organisms, as well as hospital costs and inpatient lengths of stay.

3.1.3 Assessment of Potential Risks and Benefits

While the possibility of underdiagnosis VAP is a theoretical concern, this trial does not prohibit ordering of diagnostic tests, prescription of antibiotics or microbiology lab culture workflows. Rather, it 1) utilizes behavioral “nudges” to disincentivize ordering diagnostic tests which do not meaningfully alter Bayesian diagnostic probability; 2) improves/standardizes sampling methods for respiratory cultures to decrease the frequency of false positive test results; and 3) provides frontline providers with data (degree of alveolar neutrophilia) to better inform culture interpretation and management decisions. All of these interventions components are within what is considered the standard of care and supported by expert consensus guidelines to inform clinical decision making, however they have not been

operationalized/implemented in a standardized fashion as proposed by this study.^{9,10} Counterbalanced with the significant harms of overuse of antibiotics, on the whole the potential benefits of this study intervention significantly outweigh its potential risks.

This study's endpoints have been calibrated to reflect safety concerns and will track rates of mortality, ventilator usage and ventilator-associated events to monitor for important safety signals. Importantly, systematic reviews of other antimicrobial stewardship interventions in ICUs (predominantly prospective audit and feedback) have shown stewardship interventions to be safe.⁷³ In total, there are multiple *immediate* potential benefits to patients exposed to this intervention and the potential *long-term* benefits to patients from information gained from this trial are significant.

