6 STUDY POPULATION

6.1 INCLUSION CRITERIA

This pilot/feasibility trial will occur within the Michigan Medicine Cardiac Care Unit (CCU, 7D) and the Michigan Medicine Critical Care Medicine Unit (CCMU, 6D). This study will not be screening or enrolling individual patients, but rather instituting system-based interventions in the diagnostic testing workflow that providers engage with as part of routine clinical care. Study subjects in this trial are therefore all patients hospitalized in the aforementioned Michigan Medicine ICUs during the study period requiring invasive mechanical ventilation, as well as healthcare providers providing care to said patients in the aforementioned ICUs during the study period.

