7 STUDY INTERVENTION(S)

7.1 STUDY INTERVENTION(S) ADMINISTRATION

7.1.1 Study Intervention Description

This study's VAP diagnostic stewardship bundle will include interventions that occur at discrete phases in the diagnostic testing pathway: 1) the *preanalytic phase*, in which tests are ordered; 2) the *analytic*

phase, in which diagnostic specimens are collected and laboratory tests are performed; and 3) the postanalytic phase.

Trial Interventions

Diagnostic Testing Phase	Intervention	Implementation method	Details
Respiratory culture ordering	CDS tool requiring providers to select a valid indication for respiratory culture performance : 
 • New radiographic infiltrate on CXR or chest CT • Purulent endotracheal secretions • Worsening PEEP and/or FiO2 	Interruptive EHR alert triggered upon respiratory culture order, tagged to custom CDS order set.	The following prompts were given to providers using the CDS order set: 
 • Fever or leukocytosis without aforementioned culture indications is unlikely to indicate pneumonia. • Radiographic infiltrates consistent with atelectasis or pulmonary edema do not require respiratory cultures. • Purulent secretions are different than thickened or increased nonpurulent secretions (the latter do not require cultures). • Transient worsening of PEEP or FiO2 that rapidly improves is unlikely to indicate pneumonia
Respiratory culture collection	CDS tool requiring providers to use non-bronchoscopic BAL (performed by respiratory therapists) when no contraindications present. All BAL specimens automatically sent for quantitative respiratory culture & cell count/differential .	Interruptive EHR alert triggered upon respiratory culture order, tagged to custom CDS order set	Contraindications to BAL were as follows: 
 • major lung surgery in prior 30 days • gross blood in endotracheal secretions • INR>2 • platelet count <50k • P/F ratio <80. Consideration of bronchoscopy was recommended for sampling upper lobe infiltrates.

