3. Reporting (postanalytic) phase:

- *Study intervention:* In participating ICUs, all providers who order respiratory cultures will be automatically routed to a custom study order set within the electronic medical record. This order set will require performance of BAL for all patients without exclusion criteria (see Section 4.1) in whom respiratory cultures are ordered. The order set will include not only an order for respiratory culture from BAL (performed by the Michigan Medicine Clinical Microbiology lab), but also a BAL cell count and differential. The Michigan Medicine Clinical Microbiology lab will work up all respiratory cultures according to current practices, but will not release the culture reports to providers for samples in which the BAL neutrophil % is less than 50%. When providers examine the culture result in the electronic medical record, an automated message will indicate that the BAL neutrophil % is low on the sample, making pneumonia exceedingly unlikely. Providers will be informed in this automated message that they can call the Michigan Medicine Clinical Microbiology lab and manually request release of the results if they feel it is indicated.

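### The unit-wide safety endpoints dilute harm from withheld culture reports below practical detection, and no planned analysis or DSMB metric looks at the patients concerned

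*Combined protocol and SAP*

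**What the plan says.** Section 3.1.1 (Known Potential Risks) states the risk: "A potential concern for any intervention aimed at lowering overdiagnosis is the possibility of" underdiagnosis. It adds that "Expedient performance of respiratory cultures and receipt of susceptibility test results is a key component of VAP management". Section 3.1.3 answers that the study's "endpoints have been calibrated to reflect safety concerns and will track rates of mortality, ventilator usage and ventilator-associated events".

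The three primary endpoints (Section 1.1 and Section 4) are a death rate, a ventilator-associated event (VAE) rate and median ventilation duration. Section 6.1 defines the population as "all patients hospitalized in the aforementioned Michigan Medicine ICUs during the study period requiring invasive mechanical ventilation". Section 9.2 compares one intervention year with five earlier years. Section 9.4.1 gives the DSMB the same three metrics per ICU every two months. Section 9.4.2 adds subgroups by ICU and by implementation phase, the latter matched on calendar months.

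The reporting step starts six months into the intervention year (Section 5.1). Under Section 7.1.1 the laboratory "will work up all respiratory cultures according to current practices, but will not release the culture reports to providers" when BAL neutrophils are below 50%; providers may call to have a result released. Section 2.2 supports the cut-off by stating that "BAL neutrophil percentage <50% has a negative predictive value of 92% for ruling out VAP". The neutrophil result is otherwise used only as a feasibility percentage, which the synopsis words as "Percentage of respiratory cultures from BAL samples with alveolar neutrophils <50% (for Phase 2 only" (the bracket closes there).

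**The concern.** The reporting step can act only on patients whose report is withheld. They are a fraction of those cultured, who are themselves a fraction of those ventilated. Every safety measure in the plan averages over all ventilated patients, so an excess of deaths or VAEs in the withheld group is divided by a much larger denominator. Median ventilation duration hardly moves when a small share of patients changes.

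Nothing in the plan asks what the withheld cultures grew, how often release was requested, when treatment began, or what happened to these patients. The primary objective is safety. The trial could therefore report preliminary safety without having looked at the patients exposed to its most novel step, and the DSMB would have no view of them during the trial.

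**Working it through.** The documents give no sample size, power, event count or margin, so there is no design figure to reproduce. The textual part of the point needs no arithmetic. The steps below give only its scale.

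**1. VAP among withheld results (m).**
- From the stated 92% negative predictive value: m = 1 − 0.92 = 8%. Section 2.2 says that this comes from a VAP-enriched population.
- From the 95% sensitivity in the suppression message (Section 7.1.1) and the 10% prevalence among ventilated patients (Section 2.2): m = (1 − Se)·p / [(1 − Se)·p + Sp·(1 − p)]. Specificity is not given. With an assumed Sp of 0.3, m = 0.005/(0.005 + 0.27) = 1.8%. With Sp of 0.7, m = 0.005/(0.005 + 0.63) = 0.8%.
- Neither is clearly the better input. The 10% refers to all ventilated patients, but those reaching BAL have passed an ordering screen for pulmonary signs. The message also limits its sensitivity to non-neutropenic patients, while Section 6.2 lists no exclusions for the reporting step. I carry m = 1–8%.

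**2. Dilution.** Let s be the share of ventilated patients with a withheld result in Phase 2, and d the excess mortality in a missed VAP. Both are assumed: s = 2–20%, d = 10–50 points.
- Excess among withheld patients = m·d
- Excess in the Phase 2 stratum = s·m·d
- Excess in the year-long comparison = 0.5·s·m·d, because the step runs for about half the year

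| s | m | d | withheld group | Phase 2 | full year |
|---|---|---|---|---|---|
| 2% | 1% | 10 | 0.1 | 0.002 | 0.001 |
| 10% | 8% | 30 | 2.4 | 0.24 | 0.12 |
| 20% | 8% | 50 | 4.0 | 0.80 | 0.40 |

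(d and the last three columns are in percentage points.)

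**3. Detectability.** I assume 500–1000 ventilated patients a year, 30% mortality, 5:1 historical to intervention patients, and two-sided 0.05 (Section 9.2 does not state sidedness). The proportion dead stands in for the planned rate test.
- Power over the whole grid is 2.5–4.4% for the full year and 2.5–5.5% for Phase 2. The upper-tail error rate alone is 2.5%.
- Most favourable Phase 2 case: 500 patients against 2500, SE = √[0.21·(1/500 + 1/2500)] = 2.24 points, against an excess of 0.80.
- With baseline mortality of 20–40%, the full-year comparison has 80% power only for a rise of 4.0–6.8 points. At s = 10% this needs an excess of 4.0/0.05 = 80 to 6.8/0.05 = 136 points in the withheld group, which is impossible or nearly so. At s = 20% it needs 40–68 points.
- DSMB review is per ICU, so its numbers are smaller still.

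**4. Looking at the group directly.**
- Among 50 withheld cases, the expected number of VAPs is 4 at m = 8%, with P(at least one) = 1 − 0.92^50 = 98.5%. At m = 1% it is 0.5, with P = 39.5%.
- A formal test would also be weak: 50 against 50 gives 18% power for a 10-point excess and 53% for 20 points.
- A difference-in-differences against BALs above 50% does no better. With 135 patients in each of four cells, a generous assumption, SE = √(4·0.21/135) = 7.9 points, about twice the largest excess in the table (4.0).

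**5. Are the data there?** The collection row of the Section 7.1.1 table says "All BAL specimens automatically sent for" quantitative culture and a cell count with differential, and that step starts at study onset. The reporting-phase text of the same section places the cell count in its own order set, and the synopsis restricts the neutrophil endpoint to Phase 2. Section 4 lists that endpoint without the restriction. The reporting-phase text has all cultures worked up, whereas the suppression message ties identification and susceptibility testing to a call within 7 days. No section says that release calls are logged.

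**The case against.** The strongest reply is that this is a pilot of a population-based intervention seeking preliminary safety, so unit-level endpoints suit its objective. That stands: they should be supplemented, not replaced.

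Four stronger readings are tempting, and the documents do not support them.
- A reader might infer that the stated risk is specifically missed VAP in patients with a withheld report. Section 3.1.1 speaks of the whole bundle, including slow or absent culturing. The ordering step can also miss VAP, in patients who are never cultured.
- A reader might infer that harm from suppression is invisible. Section 9.4.2 does examine Phase 2 separately, which removes the dilution from timing. It does not remove the dilution over patients with no withheld result.
- A reader might take 8% as the rate of missed VAP. It comes from an enriched population, and a withheld result is not a missed case: results are released on request, and Section 3.1.3 says that antibiotic prescribing is not prohibited.
- A reader might treat Phase 1 BALs below 50% as a ready-made control. That depends on passages which conflict about when differentials begin.

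The weakness of a formal comparison is also a fair objection. It rules out a test as the remedy, but not a descriptive listing.

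**Conclusion.** The point holds in a limited form. On the text alone, no endpoint, subgroup or DSMB metric examines patients whose culture report was withheld, although Section 3.1.1 names the relevant risk and Section 3.1.3 says the endpoints address it.

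On scale, plausible harm from the reporting step would shift Phase 2 unit mortality by at most about 0.8 points under the assumptions above, with power barely above the error rate. That conclusion is stable across the ranges tried. The figures themselves depend on assumed patient numbers, baseline mortality, share withheld and excess mortality, none of which the documents give. This is a worthwhile, low-cost improvement to safety monitoring; it does not invalidate the planned endpoints.

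**What to change.** Add to Sections 4 and 9.4.1 a prespecified descriptive safety listing of every patient with BAL neutrophils below 50%, given to the DSMB at each meeting. It should show:
- growth on the culture;
- whether and when the result was released on request, from a log of calls;
- antibiotics started within 7 days, and the time to them;
- VAE, ventilator days and death.

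Summarise with estimates and confidence intervals, and state that no formal test is planned. Do not make a difference-in-differences the main analysis.

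Reconcile three pairs of passages:
- Section 1.1 and Section 4, on the Phase 2 restriction of the neutrophil endpoint;
- the collection row and the reporting-phase text of Section 7.1.1, on whether the differential is ordered from study onset;
- the suppression message and the reporting-phase text of Section 7.1.1, on whether withheld cultures are fully worked up without a call.

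If differentials exist from onset, show Phase 1 BALs below 50%, whose results were released, alongside as a descriptive comparator.

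The cost is protocol and SAP wording, a call log and some extraction from laboratory and health-record data. Numbers will be small and intervals wide. Patients never cultured because of the ordering step remain uncovered, so the unit-level endpoints stay as they are.
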